## Appendix 7. Required Laboratory Tests

Screen	At Each Visit	Frequency Per Table 1. Schedule Of Activities
White blood count/differential	White blood count/differential	TSH
Hemoglobin	Hemoglobin	Prothrombin time (PT or INR)
Platelets	Platelets	Urinalysis
Sodium	Sodium	Urine pregnancy test
Potassium	Potassium	
Chloride	Chloride	
Blood urea nitrogen (BUN)	Blood urea nitrogen (BUN)	
Serum creatinine	Serum creatinine	
Glucose	Glucose	
Uric acid	Uric acid	
Calcium	Calcium	
Magnesium	Magnesium	
Phosphorous	Phosphorous	
Total bilirubin	Total bilirubin	
Alanine aminotransferase (ALT)	Alanine aminotransferase (ALT)	
Aspartate aminotransferase (AST)	Aspartate aminotransferase (AST)	
Alkaline phosphatase	Alkaline phosphatase	
Total protein	Total protein	
Albumin	Albumin	

Amylase	Amylase	
Lipase	Lipase	
TSH		
Prothrombin time (PT or INR)		
Urinalysis		
Urine pregnancy test

## Protocol A6181196 Statistical Analysis Plan - Version 1.0 Final

---

### 1. AMENDMENTS FROM PREVIOUS VERSION

- N/A at this time

### 2. INTRODUCTION

This document describes the planned statistical analyses for Protocol A6181196 dated 17 June 2011. This analysis plan is meant to supplement the study protocol. Any deviations from this analysis plan will be described in the Clinical Study Report.

#### 2.1. Study Design

This study is a single arm, multi-center, multi-national, Phase I/II trial evaluating the PK, safety and preliminary anti-tumor efficacy of sunitinib in chemotherapy-naïve children and young adults diagnosed with metastatic, unresectable (without major morbidity) or recurrent GIST. The study aims to enroll 15 evaluable children aged 6 years to less than 18 years. In addition, up to 15 young adults aged 18 years to less than 21 years may be enrolled. The starting dose of sunitinib in children will be 15 mg/m^2/day for 4 weeks followed by 2 weeks with no study drug, the MTD established during the pediatric Phase 1 clinical trial conducted by the Children's Oncology Group. Intrapatient dose escalation of sunitinib will be allowed, based on tolerability. Investigators will have the option to access real time PK results to aid in dosing decisions. Sunitinib dosing for the young adults will follow approved guidelines (per current USPI and SmPC). Study treatment for all patients may continue for up to 18 cycles, equaling approximately 2 years of therapy.

#### 2.2. Study Objectives

##### Primary

- To characterize the plasma PK profile of sunitinib and its active metabolite SU012662 in children and young adults with advanced (defined as unresectable without major morbidity, metastatic or recurrent) GIST.

##### Secondary:

- To investigate whether doses greater than the established pediatric MTD are tolerated in chemotherapy-naïve pediatric patients with GIST;
- To investigate the safety and tolerability of sunitinib in children and young adults with GIST;
- To investigate the anti-tumor activity of sunitinib in children and young adults with GIST;

---

## Protocol A6181196 Statistical Analysis Plan - Version 1.0 Final

---

- To explore PK-pharmacodynamic relationships with respect to safety and efficacy in children and young adults with GIST.

### **3. INTERIM ANALYSES, FINAL ANALYSES AND UNBLINDING**

No interim analysis is planned in this study.

### **4. STATISTICAL HYPOTHESES**

The primary objective of this study is to characterize the plasma PK profile of sunitinib and its active metabolite SU012662 in children and young adults with advanced (defined as unresectable without major morbidity, metastatic or recurrent) GIST. Assuming the coefficient of variation of sunitinib clearance among pediatric patients is approximately 35%, with 15 patients, we will be able to detect 35% margin of error in sunitinib oral clearance (CL/F) with 95% confidence and 80% power. Furthermore, assuming the coefficient of variation of sunitinib clearance among young adult patients is also ~35%, a total of 30 patients will allow us to detect 25% margin of error with 95% confidence and 80% power.

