## PROTOCOL SUMMARY

Gastrointestinal stromal tumor (GIST) is a tumor of mesenchymal origin occurring in the gastrointestinal tract. GIST is a very rare and newly recognized tumor in children. Pediatric GIST has a different clinical behavior and biology than typical adult GIST. The majority of pediatric GIST occurs in females, and these tumors commonly do not bear the genetic mutations present in adults with GIST.

Sunitinib (SUTENT®) received approval from the US FDA and the European Medicines Agency (EMA) in 2006 for the treatment of GIST after disease progression on or intolerance to imatinib mesylate. Following negotiations with the EMA's Pediatric Committee (PDCO), the sponsor (Pfizer) agreed to conduct this single agent, open-label, single arm, multi-centre trial of sunitinib to investigate the use of sunitinib for the treatment of pediatric GIST, collecting safety, pharmacokinetic (PK) and efficacy data in at least 6 children aged 6 years to less than 18 years with a primary endpoint of PK parameters of sunitinib and its active metabolite SU012662.

The primary objective of this study is to characterize the plasma PK profile of sunitinib and its active metabolite SU012662 in children and young adults with advanced, unresectable GIST. Secondary objectives include evaluation of whether doses greater than the established pediatric maximum tolerated dose (MTD) are tolerated in pediatric patients with GIST, and the safety, tolerability, and anti-tumor activity of sunitinib in children and young patients with GIST. The study will explore PK-pharmacodynamic relationships with respect to safety and efficacy if data allows. The primary endpoint will be the PK parameters of sunitinib and its main active metabolite including total plasma exposure (AUC24) and oral clearance (CL/F). Secondary endpoints will include the definition of adverse events and laboratory abnormalities, the objective response rate (ORR), duration of response, progression-free survival (PFS), and the overall survival (OS) at 2 years after study enrollment. Pharmacokinetic-pharmacodynamic relationships with respect to safety and efficacy in pediatric GIST will be detailed, if data allows.

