### **3. STUDY DESIGN**

This study is a single arm, multi-center, multi-national, clinical trial evaluating the PK, safety and preliminary anti-tumor efficacy of sunitinib in children and young adults diagnosed with advanced, unresectable GIST. The study aims to enroll 6 evaluable patients aged 6 years to less than 18 years. In addition, up to 15 young adults aged 18 - <21 years diagnosed with GIST may be enrolled.

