## **9.1. Sample Size Determination**

Due to the rarity of the disease and the difficulties in identifying pediatric patient suitable for participation in this study only 6 patients will be included. The statistical power has not been calculated. Descriptive analysis approach will be adopted to report study results.

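### SAP section 4 still states 80% power for CL/F with 15 children and 30 patients; the current protocol plans 6 evaluable children and calculates no power, and the SAP's apparent formula gives about 41% with 6

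*SAP*

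**What the plan says.** SAP section 4 assumes a CV of about 35% for sunitinib clearance in children and states that "with 15 patients, we will be able to detect 35% margin of error in sunitinib oral clearance (CL/F) with 95% confidence and 80% power". With the same CV assumed in young adults, it adds that "a total of 30 patients will allow us to detect 25% margin of error with 95% confidence and 80% power". It names no test, comparator, sidedness or scale. SAP section 2.1 gives the matching enrolment target: "The study aims to enroll 15 evaluable children aged 6 years to less than 18 years". SAP section 2 identifies the protocol version it was written for ("This document describes the planned statistical analyses for Protocol A6181196 dated 17 June 2011"), and SAP section 1 records no amendments.

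The current protocol differs. Section 3 says "The study aims to enroll 6 evaluable patients aged 6 years to less than 18 years" and that "up to 15 young adults aged 18 - <21 years diagnosed with GIST may be enrolled", which makes 6 + 15 = 21 patients if both targets are met. Section 9.1 says "only 6 patients will be included. The statistical power has not been calculated" and adopts a descriptive approach. The Protocol Summary is slightly looser ("efficacy data in at least 6 children aged 6 years to less than 18 years"), but it restores neither 15 children nor a power claim.

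**The concern.** The two current documents describe different studies on the primary endpoint. One claims 80% power for paediatric CL/F; the other says that no power was calculated and plans 6 children in place of 15. SAP section 4 is the only quantitative statement of power or precision for that endpoint in either document. Someone reading the SAP alone would credit the paediatric CL/F estimate with a reliability that was worked out for two and a half times as many children (15 / 6 = 2.5). That estimate is then to be compared with historical adult GIST data (Protocol section 9.2, SAP section 9.1.1), so how uncertain it is expected to be matters to the reader.

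**Working it through.** **Inputs.** From SAP section 4: CV 35% (SD taken as 0.35 of the mean), 95% confidence, 80% power, a 35% margin with 15 children, and a 25% margin with 30 patients. From Protocol section 3: 6 children. Assumption, because the SAP is silent: two-sided 5% (z = 1.960; z for 80% power = 0.842).

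**Step 1: reproduce the SAP's figures.** For two equal groups of size n, SE = 0.35 × √(2/n), detectable difference = (1.960 + 0.842) × SE, and power = Φ(difference/SE − 1.960).

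- n = 15: SE = 0.1278; detectable difference 35.8%; power for 35% = Φ(2.739 − 1.960) = 78.2%.
- n = 30: SE = 0.0904; detectable difference 25.3%; power for 25% = Φ(2.766 − 1.960) = 79.0%.

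Both match the stated 35%, 25% and 80% closely. A one-sample test against a fixed value does not: it gives 94.9% (t) or 97.2% (z) with 15, and 96.6% or 97.5% with 30. Nor does reading the margin as a 95% CI half-width, t × 0.35/√n, which is 19.4% with 15 and 13.1% with 30, far inside the stated margins.

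**Step 2: the same calculation with 6 children.** SE = 0.35 × √(2/6) = 0.2021. Power for 35% = Φ(1.732 − 1.960) = 41.0%, or 34.7% by the t distribution. The difference detectable with 80% power is 2.802 × 0.2021 = 56.6%, about 57%.

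**Step 3: how far this depends on the reading.** Power for a 35% difference at CV 35%:

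| Reading | 6 children | 15 children |
|---|---|---|
| Two-sample, equal groups, two-sided z | 41.0% | 78.2% |
| Two-sample, equal groups, log-scale increase, one-sided z | 45.4% | 78.0% |
| One-sample, two-sided t | 50.7% | 94.9% |
| One-sample, two-sided z | 68.8% | 97.2% |
| One-sample, one-sided z | 78.9% | 98.7% |
| One-sample, log-scale decrease, two-sided t | 70.1% | 99.5% |
| One-sample, log-scale decrease, two-sided z | 87.4% | 99.8% |
| One-sample, log-scale decrease, one-sided t | 84.3% | 99.9% |
| Against an assumed 50 historical adults, log-scale decrease, two-sided t | 82.1% | 98.9% |

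Only the first two rows come near 80% with 15 children, and they give 41% and 45% with 6. The readings that exceed 80% with 6 children give about 99% or more with 15, so they are not what SAP section 4 calculated.

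**Step 4: precision with 6 children.** Log-scale SD = √ln(1 + 0.35²) = 0.340. With t = 2.571 on 5 degrees of freedom, the CI factor is exp(2.571 × 0.340/√6) = exp(0.357) = 1.43. The 95% CI for geometric mean CL/F is therefore about 0.70 to 1.43 times the estimate. It would be 0.77 to 1.29 at an assumed CV of 25%, and 0.61 to 1.64 at an assumed CV of 50%.

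**The case against.** The strongest reply is that this is outdated text and not a statistical error. The SAP says which protocol version it serves, makes its claim for 15 children and says nothing about 6. The protocol's document history records that the reduction from 15 to 6 was made in 2017 and agreed with the EMA's Pediatric Committee. The current protocol disclaims power, and the analysis is descriptive, with no test, interim look or success criterion tied to section 4. That history also reports six children already included and further enrolment unlikely, so recruitment cannot respond. The observed CI will be reported where appropriate.

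Most of this stands, and it limits the consequence. It does not remove the contradiction. Protocol section 9 allows the SAP to modify the protocol's plans, but an SAP written for a 2011 protocol cannot be a deliberate departure from a target set in 2017.

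Three stronger readings are tempting, and the documents do not support them:

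- **That 6 children cannot reach 80% on any calculation.** Section 4 gives no formula, and some log-scale readings of a 35% decrease do exceed 80%.
- **That the SAP's figures were miscalculated.** They are close to correct for 15 and 30.
- **That the pooled set is also underpowered.** With 21 patients and a 25% margin, the two-sample normal calculation gives 63.9%, but a one-sample t gives 87.5%. The result depends on an unstated formula and on how many young adults enrol.

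**Conclusion.** The point holds as a mismatch between the current documents. The sample size and power in SAP section 4, and the target in SAP section 2.1, are out of date. On the two-sample normal calculation that reproduces the SAP's figures, power for a 35% difference in paediatric CL/F falls from about 78% with 15 children to about 41% with 6. This rests on the SAP's CV of 35%, a two-sided 5% level and a comparator of equal size, none of which except the CV is stated plainly in the SAP. The mismatch itself is certain; the exact shortfall depends on the reading. No analysis or decision changes. What is affected is the power or precision stated in advance for the paediatric CL/F estimate.

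**What to change.** In SAP section 4, delete the power statements for 15 and 30 patients, state that no power is claimed, and give the expected precision for 6 children. Suggested content: assuming a CV of 35% and a simple log-scale t-interval on individual CL/F estimates, the 95% CI for geometric mean CL/F in 6 evaluable children is expected to run from about 0.70 to 1.43 times the estimate. Say that this is approximate, because under Protocol section 7.1 CL/F comes from a population PK model. Omit a pooled figure, since the number of young adults is open. Update the enrolment target in SAP section 2.1 and the protocol version cited in SAP section 2.

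The deletion and the alignment are needed for consistency. The precision sentence fills the gap that the deletion leaves. The cost is SAP wording only, with no new patients, data or analyses. The downside is a less favourable precision on record.

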### **5. ANALYSIS SETS**

#### **5.1. Full Analysis Population**

The full analysis (or intent-to-treat) population will include all enrolled patients regardless of what treatment, if any, was received. The efficacy analysis will be based on the full analysis population.

#### **5.2. Per Protocol Population**

The per protocol (or as-treated) population will include all enrolled patients who receive at least one dose of study drug. The safety analysis will be based on per protocol population.

#### **5.3. Pharmacokinetic population**

The pharmacokinetic (PK) population will include all treated patients with at least one PK observation. The pharmacokinetic analysis will be based on pharmacokinetic population.

#### **5.4. Protocol Deviations**

Changes to the procedures that may impact the quality of the data will be considered significant protocol deviations. These changes would include any circumstances that would alter the evaluation of the pharmacokinetics, safety or efficacy of the study. Examples include but may not be limited to, violations to the inclusion/exclusion criteria, non-compliance to study drug administration, and incomplete tumor assessments.

---

## Protocol A6181196 Statistical Analysis Plan - Version 1.0 Final

---

In the case of a significant protocol deviation, the situation will be evaluated on a case-by-case basis and data collected during the affected treatment period may be excluded from the analysis.

## 6. ENDPOINTS

### 6.1. PRIMARY ENDPOINT

- Pharmacokinetic parameters of sunitinib and its main active metabolite (SU012662) including total plasma exposure (AUC24) and oral clearance (CL/F).

### 6.2. Secondary ENDPOINTS

- Type, incidence, severity (graded by the National Cancer Institute (NCI) Common Terminology Criteria for Adverse Events [CTCAE], Version 4.0 [v4.0]), timing, seriousness, and relatedness of adverse events and laboratory abnormalities;
- Objective response rate, duration of response, PFS and OS at 2 years after study enrollment;
- Pharmacokinetic-pharmacodynamic relationships with respect to safety and efficacy in pediatric GIST.

## 7. COVARIATES AND STRATIFICATION FACTORS

### 7.1. Covariates

The potential influence of baseline patient characteristics such as age, gender, ethnicity, and tumor characteristics (including *KIT* genotype, etc.) on primary and secondary endpoints may be evaluated if necessary.

### 7.2. Stratification Factors

None.

## 8. HANDLING OF MISSING VALUES

Pharmacokinetic and safety endpoints will not be imputed for missing data. For efficacy endpoints, non-event observations will be censored according to the censoring rules specified in Section 9.

---

## Protocol A6181196 Statistical Analysis Plan - Version 1.0 Final

---

**Missing Dates:** In compliance with Pfizer standards, if the day of the month is missing for any date used in a calculation, the 1st of the month will be used to replace the missing date unless the calculation results in a negative time duration (e.g., date of onset cannot be prior to Day one date). In this case, the date resulting in 0 time duration will be used. Pfizer standards are also used if both month and day are missing (Jan 1 unless negative time duration).

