**17. Echocardiogram or MUGA scan** at screening, then on Day 1 of every 3rd cycle (for example, Day 1 Cycle 3, Day 1 Cycle 6 ..etc.). As clinically indicated at the end of treatment/withdrawal per [Section 6.3.1](#) and see suggested dose modifications guidelines for left ventricular systolic dysfunction in [Section 5.2.10](#).

18. Adverse Events: Patients must be followed for adverse events from the first day of study treatment until 28 days after the last dose of study treatment, or until all serious or study drug-related toxicities have resolved or are determined to be “chronic” or “stable,” whichever is later. Serious adverse events should be monitored and reported from the time that the patient provides informed consent as described in the protocol.

19. Study Drug Compliance: Unused sunitinib will be returned to clinic for drug accountability at the beginning of each subsequent cycle.

20. Concomitant Medications/Treatments will be recorded from 28 days prior to the start of study treatment, during the study and up to 28 days after the last dose of sunitinib.

21. Follow-up Survival Monitoring: Follow-up survival information, including post-study anti-cancer treatment, will be collected by clinic visit or telephone contact every 3 months until death, or either 24 months from patient’s first dose of study treatment or completion of 18 cycles. See Section 6.3.2.

22. Growth and Pubertal Maturation Assessments (for pediatric patients only): Bone age assessments must be performed at screening, and then annually with an additional test at End of Treatment or until growth plate closure. Tanner staging must be performed at screening. If patient is Tanner Stage 1-4, then Tanner assessment should be repeated every 6-9 months and at End of Treatment or until patient reaches Tanner Stage 5. Refer to Section 7.3 Growth and Pubertal Maturation Assessments. Tanner staging assessments can only be waived upon agreement by Pfizer. If Tanner staging is initiated it should be continued per Section 7.3.

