## Protocol A6181196 Statistical Analysis Plan - Version 1.0 Final

---

tumor assessment documenting absence of progressive disease for patients who 1) are given anti-tumor treatment other than the study treatment prior to observing objective tumor progression; 2) are removed from the study prior to documentation of objective tumor progression; 3) are ongoing at the time of the analysis.

Patients who do not have any post-baseline tumor assessments will have their PFS endpoint censored on the date of enrollment. Death or disease progression that occurs after more than one missed visit will be censored on the day following the date of the last tumor assessment as well.

PFS will be summarized using Kaplan-Meier methods and displayed graphically where appropriate. Median PFS and its corresponding 2-sided 95% CI for the median will be provided.

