### **9.1.2.4. Overall Survival**

Overall survival (OS) is defined as the time from enrollment to the date of death due to any cause. OS data will be censored on the day following the date of the last contact at which the patient is known to be alive. OS will be summarized using Kaplan-Meier methods and displayed graphically where appropriate. The median survival time and 2-sided 95% CI for the median will be estimated.

The 2-year survival probability will be estimated using the Kaplan-Meier method and a 2-sided 95% CI will be constructed for the 2-year survival probability.

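### The SAP's partial-date rule can place a death before the patient was last known alive and, if it is also used to order new therapy against progression, can turn a PFS event into a censored time

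*SAP*

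**What the plan says.** SAP Section 8 (Missing Dates) covers every partial date with one rule. It applies "if the day of the month is missing for any date used in a calculation", and the 1st "of the month will be used to replace the missing date unless the calculation results in a negative time duration". On the exception it adds: "In this case, the date resulting in 0 time duration will be used". If month and day are both missing, 1 January is used, with the same exception. There is no separate rule for deaths, last contacts, progressions or the start of new therapy. The efficacy rules in SAP Section 9 do not mention partial dates, and the protocol has no partial-date rule of its own.

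Two endpoint definitions meet this rule:

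- **OS (SAP 9.1.2.4).** "Overall survival (OS) is defined as the time from enrollment to the date of death due to any cause". For censoring, "OS data will be censored on the day following the date of the last contact at which the patient is known to be alive".
- **PFS (SAP 9.1.2.2).** A patient given "anti-tumor treatment other than the study treatment prior to observing objective tumor progression" is censored the day after the last progression-free tumor assessment.

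On data collection, Protocol Table 1, footnote 21, says: "Follow-up survival information, including post-study anti-cancer treatment, will be collected by clinic visit or telephone contact every 3 months until death". Protocol 6.3.2 likewise has survival status and new anti-cancer therapy recorded by telephone or visit.

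**The concern.** An earliest-date rule is safe only if each imputed date is checked against what else is known about the patient. Here the sole check is on the sign of a duration. For a death, that duration starts at enrollment, so an impossible date (death before a recorded contact alive) passes. The date needed for a proper check is already collected, because OS censoring uses it.

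For PFS the issue is order. Whether a progression is an event or a censored time depends on whether new therapy came first. If a therapy date with a missing day is set to the 1st, therapy that followed a progression in the same month appears to precede it.

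PFS and OS at 2 years are named secondary endpoints, and the pediatric subgroup is planned at 6, so a single misplaced date can be visible in the estimate.

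**Working it through.** The plan states no figure to reproduce. The check is to apply the SAP Section 8 rule literally: imputed date = the later of (1st of the month, or 1 January) and the enrollment date. All dates and lags below are assumptions chosen for illustration.

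**1. Death.** Enrolled 10 Jan 2014, last known alive 18 Sep 2014 (day 251 from enrollment), died 25 Sep 2014 (day 258).

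- Day missing: death imputed to 1 Sep, day 234. That is 251 − 234 = 17 days before the patient was last known alive.
- Month and day missing: 1 Jan 2014 precedes enrollment, so the exception sets OS to 0 days.
- The exception can itself create the error. Enrolled 10 March, alive 20 March, died in March with the day missing: death is imputed to 10 March.

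Maximum backward shift from the true date: 31 − 1 = 30 days with the day missing; 31 December to 1 January = 364 days (365 in a leap year) with the month missing too. Averaged over all calendar days of 2012–2017, the mean shift is 14.7 and 182 days.

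**2. Progression, if the rule is used for ordering.** Same enrollment date, taken as first dose. Cycles are 42 days (Protocol 5.2.3), with scans near Day 28 of even cycles (Protocol 7.4).

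- Clean scan at Cycle 2 Day 28: 42 + 28 = study day 70, which is 69 days from enrollment, 20 March.
- Progression at Cycle 4 Day 28: 126 + 28 = study day 154, which is 153 days from enrollment, 12 June.
- New therapy truly started 26 June. With the day missing it becomes 1 June; with the month missing too it becomes 10 January (enrollment). Both precede 12 June.
- Result: the event at 153 days becomes a censored time at 69 + 1 = 70 days.

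**3. How often the order reverses, given that the second date is partial.** The same calculation serves contact-to-death and progression-to-therapy. With the day missing, reversal needs both dates in one month and the first date after the 1st. For a 30-day month and a lag of L days (up to 28) the share is (29 − L)/30; for L = 14 it is 15/30 = 50%. With the month missing as well, the share in a 365-day year is (364 − L)/365; for L = 14 it is 350/365 = 96%. Over the actual calendar:

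| Assumed lag (days) | Day missing | Month and day missing |
|---|---|---|
| 7 | 74% | 98% |
| 14 | 51% | 96% |
| 21 | 28% | 94% |
| 28 | 5% | 92% |
| 45 | 0% | 87% |
| 91 | 0% | 75% |

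These are conditional on a partial date. The documents do not say how common partial dates are.

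**4. Effect on the curve.** A Kaplan-Meier step equals the current estimate divided by the number at risk. With no earlier event that is 1/n: 1/6 = 16.7 points with all 6 children at risk, 1/4 = 25 points if two were censored earlier, and 1/21 = 4.8 points in a pooled analysis with all 15 possible young adults.

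**The case against.** The best defense concerns PFS. The rule speaks of dates used in a calculation, and its exception and example are about durations. The new-therapy date enters no PFS duration; it matters only for a question of fact, namely which came first. The SAP never says to answer that with an imputed date. Protocol 6.4 lists disease progression and the need for other anti-cancer therapy as separate reasons for withdrawal, so the record may settle the order. This stands to the extent that the PFS consequence is conditional. It does not remove the point, because the SAP does not exclude the use and its wording reaches any date.

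The second defense is low consequence. PFS and OS are secondary, reporting is descriptive (Protocol 9.1), and SAP Section 9 runs time-to-event analyses only if events suffice. Deaths in the safety reporting period must be reported (Protocol 8.2, 8.13.1), and Protocol 6.4 asks for every effort to document outcome. All of this limits the impact. None of it makes an impossible death date correct.

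A reader might also infer stronger claims that the documents do not support:

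- **That 2-year survival would shift by 16.7 points.** Dates move only earlier, so crossing the mark needs a recorded death after 2 years. Follow-up stops at 24 months from first dose or at completion of 18 cycles; 18 × 42 = 756 days, about 26 days past 730, plus any gap from enrollment to first dose. The case is narrow. Nor is 16.7 an upper bound, as step 4 shows.
- **That PFS is biased upward.** Partial progression or death dates moved earlier shorten PFS, and a death after more than one missed visit could be pulled back and counted as an event. The net direction is undetermined.
- **That month-only dates are likely.** Collection every 3 months by telephone or visit makes them plausible, no more.

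**Conclusion.** The OS point holds on the SAP's own text. Followed exactly, the rule can give a death date that other collected data contradict: up to 30 days early, 364 or 365 days early, or at OS of zero. Every death imputed this way falls on or before its true date, but only partial death dates are affected.

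The PFS point holds conditionally. If date ordering is treated as a calculation under SAP Section 8, a partial therapy date in the same month as an earlier progression (the same year, if the month is missing) can turn a true event into a censored time.

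The size in practice is unknown because no rate of partial dates is given. One changed event moves the curve by about 1/(number at risk), for example 16.7 points with all 6 children at risk. This is worth correcting because it is a stated rule giving a wrong result and the correction is cheap. It does not touch the primary pharmacokinetic endpoint.

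**What to change.** Keep the general rule and add three lines to SAP Section 8:

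- **(a) Death.** Use the later of the imputed date and the last date known alive. In the worked case this gives 18 September (day 251, against a true 258) whether or not the month is known. Do not use the day after: for a patient alive on 30 September with death recorded in September, it would give 1 October and contradict the recorded month.
- **(b) Last contact.** Never impute earlier than the last documented visit, scan or dose.
- **(c) New therapy against progression.** Do not decide the order with an imputed date. Use the recorded part of the date and other records (last study dose, reason for discontinuation). If the order is still unresolved, count the progression as an event and report the result with it censored as a sensitivity check. In the worked case, even if other records were silent, the event at 153 days is kept.

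Imputing therapy to the last day of the month is not a safe shortcut. With therapy truly on the 3rd and progression seen on the 20th, it would count an event that SAP 9.1.2.2 censors.

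The cost is a little programming. Under (c), an unresolved case may occasionally count an event that truly followed new therapy; the sensitivity check shows the effect. The data are already collected. The SAP needs updating anyway, since its Section 2.1 still plans 15 children where the current protocol plans 6.
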